9.5. Data Sources

Sources to be analyzed for data collection include subject's clinical files and prescription / laboratory / pharmacy files and accounting data.

Centers participating in the Adherence study have to have the complete history (within the observation period) of pharmacy refills available electronically.

For centers participating in the Prescription errors sub-study, registration of ART errors, in either paper or electronic format, is required.

9.6. Study Size

Adherence study

The sample size needed to achieve a power of 80% for detecting a difference of 0.02 in the proportion of patients with adherence > 90% (adherent patients) between the two cohorts, with a two sided test with a significance level of 0.05, was determined using the methodology proposed by Sahai and Khurshid {27760}. The number of discordant pairs (the ones with more than 90% adherence in only one of the 2 cohorts) was estimated using data reported in Airoldi et al.{16102}. In this study patients in a non-STR regimen had an average adherence rate of 97% and after changing to an STR regimen a rate of 98%. Assuming the reported standard deviation of 11%, a 0.74 and 0.77 proportion of adherent patients was estimated for non-STR and STR regimens, respectively, which represent the marginal probabilities of adherence. Therefore, if one assumes that patients who adhere to non-STR also adhere to the STR regimen, the probability of adherence to STR conditional to non-adherence to non-STR and non-adherent to STR.

Since a multivariate analysis will be performed, the suggestion by Katz {27773} of adding 10 observations per covariate included in the logistic regression was considered. A potential 20% loss of patient-regimens due to missing values on covariates was considered, as well as an inclusion of 10 covariates in the logistic regression model. In addition a 15% oversampling on the non-STR cohort was considered to enable a final sample size, post PSM, of 1030 pairs of patient-regimens. Hence 700 subjects will need to be included in the STR cohort and 805 subjects will need to be included in the non-STR cohort.

A preliminary evaluation of the availability of the centers to collect data was performed. Taking into account this information, an average of 80 subjects in the STR cohort and 90 subjects in the non-STR cohort, will be needed per center to achieve the power considered in the sample size determination presented above. It is possible that some centers will have less than 80 subjects to include in the STR cohort. In those cases, data from all these subjects should be collected and

other centers may include more than 80 subjects to ensure the overall 2060 patient-regimens sample size is reached.

Prescription errors sub-study

Due to the nature of the study design, a formal sample size determination was not performed. Each center will collect data on approximately 40 hospitalization episodes randomly selected as described in the 'Setting' section.

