	• Confounder adjusted actual (i.e. OIA adjusted) monthly ART plus hospitalization costs by patient-regimens adherence level (NA and OIA)	
	• Proportion of hospitalization episodes with ART prescription errors overall and in STR versus non-STR groups	
	• Percentage of prescription errors, overall and STR versus non- STR.	
	The list of confounders to be included is detailed in the variables to be collected section. All variables collected will be considered as confounders except the dependent or related dependent variable in question for each endpoint.	
Data Sources:	Centers participating in the Adherence study must have the complete history (within the observation period) of pharmacy refills available electronically in the hospital records. Subjects' clinical records will be the main source for the remaining data to be collected.	
	For centers participating in the Prescription errors sub-study, registration of ART errors, in either paper or electronic format, is required. The main source of data is thus the subject clinical record.	
Study Size:	Adherence study	
	700 STR subjects and 805 non-STR subjects is the sample size needed to enable a final sample size for analysis of 2060 patient-regimens (assuming an average of 1.5 patient-regimens per subject), after matching on a variable ratio with a propensity score approach. This is necessary to achieve a power of 80% for detecting a difference of 0.02 in the proportion of subjects with adherence > 90% between the two cohorts, with a two sided test with a significance level of 0.05, determined using the methodology proposed by Sahai and Khurshid {27760}.	
	Prescription errors sub-study	
	Due to the nature of the study design a formal size determination could not be performed. Each center will aim to include 40 inpatient care episodes of HIV-1 infected subjects that occurred between 1st	

	January 2012 and 29th December 2013. There is no minimum number of subjects required since the unit of observation is the hospitalization episode. The subjects enrolled onto the sub-study do not need to be participating in the adherence study in order to be eligible.	
Data Analysis:	Baseline characteristics will be reported using descriptive statistics. In general, when presenting descriptive statistics, the following parameters will be presented:	

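### The adherent proportions 0.74 and 0.77 behind the sample size do not fit the means and SD they are derived from if adherence cannot exceed 100%; the effect on power is undetermined

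*Protocol*

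**What the plan says.** The primary endpoint is binary: adherence above 90%, compared between STR and non-STR as an odds ratio (synopsis and section 9.1). Section 9.6 sizes the study for 80% power, "with a two sided test with a significance level of 0.05", for "detecting a difference of 0.02 in the proportion of patients with adherence > 90% (adherent patients) between the two cohorts". The synopsis repeats the 80% power and the 0.02 difference.

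Section 9.6 has no observed proportion above 90%. It starts from a cited switch study: "patients in a non-STR regimen had an average adherence rate of 97% and after changing to an STR regimen a rate of 98" per cent. It continues: "Assuming the reported standard deviation of 11%, a 0.74 and 0.77 proportion of adherent patients was estimated for non-STR and STR regimens, respectively". These two values are then taken as the marginals of the matched pair. The protocol assumes that anyone adherent on non-STR would also be adherent on STR, and uses this to obtain the discordant pairs. The sentence that would give the resulting discordance is broken in the text available. After an allowance for 10 covariates and a 20% loss to missing covariates, the final size is 1030 pairs of patient-regimens.

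No distribution is named for the step from mean and SD to proportion. Section 7.2 defines non-adherence and overall inadequate adherence as proportions of days in the regimen period.

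**The concern.** A mean of 97% or 98% with an SD of 11% cannot come from a symmetric distribution on a scale that stops at 100%. It needs a large mass near 100% and a long lower tail. A normal conversion spreads patients above the ceiling and, to keep the mean, puts too many below 90%.

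These two proportions are the only baseline values the protocol gives for its primary endpoint, and they feed the discordant pairs directly. If they cannot be true together with the means and SD they come from, the reader has no valid basis for the 80% power.

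**Working it through.** **Inputs (section 9.6).** Means 97 (non-STR) and 98 (STR); SD 11 for both; threshold 90; difference 0.02; two-sided 0.05; 80% power; 10 covariates at 10 observations each; 20% loss; 1030 pairs.

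**1. Reproducing the printed proportions.** With a normal curve, P(X > 90) = Φ((mean − 90)/SD).
- Non-STR: Φ(7/11) = 0.738, printed as 0.74.
- STR: Φ(8/11) = 0.766, printed as 0.77.

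The normal curve is an inference, but it returns both figures to two decimals. The same curves give P(X > 100) = 1 − Φ(3/11) = 0.39 and 1 − Φ(2/11) = 0.43.

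**2. What the means and SD allow on a 0–100% scale.** Let Y = 100 − adherence, so 0 ≤ Y ≤ 100. The function 0.11y − 0.001y² is concave and equals 0 at y = 0, 1 at y = 10 and 1 at y = 100. It is therefore at least 1 wherever 10 ≤ y ≤ 100 and never negative below that. Hence

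P(adherence ≤ 90) = P(Y ≥ 10) ≤ 0.11·E[Y] − 0.001·E[Y²], with E[Y²] = SD² + E[Y]².

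| | E[Y] | E[Y²] | Largest share ≤ 90% | Smallest share > 90% | Printed |
|---|---|---|---|---|---|
| Non-STR | 3 | 121 + 9 = 130 | 0.33 − 0.130 = 0.200 | 0.800 | 0.74 |
| STR | 2 | 121 + 4 = 125 | 0.22 − 0.125 = 0.095 | 0.905 | 0.77 |

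Linear programming over all distributions on 0–100 with these moments confirms the bounds as sharp and gives upper limits of about 0.99 in both cohorts. For STR at exactly 98%, the mean alone already excludes 0.77: an average shortfall of 2 points allows at most 2/10 = 20% at or below 90%.

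**3. Rounding.** The means and SD are printed as whole numbers, so take the most favourable values that round to them.
- STR, 97.5 and 10.5: E[Y] = 2.5, E[Y²] = 110.25 + 6.25 = 116.5, bound 0.275 − 0.1165 = 0.1585. At least 0.84 are adherent, so 0.77 stays excluded.
- Non-STR, 96.5 and 10.5: E[Y] = 3.5, E[Y²] = 110.25 + 12.25 = 122.5, bound 0.385 − 0.1225 = 0.2625. At least 0.7375 are adherent, so 0.74 is just reachable. This needs both inputs at the edge of rounding and some patients at 0% adherence.

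**4. A bounded illustration.** Beta distributions with means 0.97 and 0.98 and SD 0.11 give P(> 0.9) = 0.924 and 0.961, a gap of 0.037. With discordance ψ = 0.0372 and d = 0.02, the matched-pair (McNemar) formula

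n = [1.96·√ψ + 0.84·√(ψ − d²)]² / d²

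gives 727 pairs. Taking the allowances as 100 added and then division by 0.8, (727 + 100)/0.8 = 1034, close to the printed 1030.

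**5. Sensitivity.** Power for d = 0.02 at assumed discordances, none of them the protocol's own figure:

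| Discordance | 1030 pairs | 824 pairs (1030 × 0.8) |
|---|---|---|
| 0.037 (beta gap) | 92% | 85% |
| 0.04 | 90% | 82% |
| 0.05 | 82% | 73% |

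**The case against.** Several points on the other side stand.

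- **The ceiling is an assumption about the cited study.** Section 9.6 does not give that study's scale. The protocol's own NA and OIA are proportions of days, but its primary endpoint is described as a medication possession ratio, for which no cap is stated. The point is therefore conditional.
- **The two figures do not fail equally.** The 0.77 fails throughout the rounding range, although at a mean of 97.5% it takes the SD as well as the mean to exclude it. The 0.74 fails at the printed values but not at the extreme rounding corner.
- **The discordance used cannot be read.** A discordance equal to the printed gap of 0.03 gives 586 pairs, and (586 + 100)/0.8 = 858, not 1030. So no power figure can be attributed to the plan beyond its own 80%.

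A reader might infer that the study is underpowered. The documents do not support this: matched-pair power depends on the discordance and the 0.02 difference, and the beta illustration returns almost the printed size. Nor can the gap between the two lower bounds, 0.905 − 0.80 = 0.105, serve as a discordance for a 0.02 difference. Under the nesting assumption discordance and difference are the same quantity, and both cohorts would have to sit at their extremes at once. The beta calculation also sets a gap in marginals beside a 0.02 target, so it shows scale and is not a corrected size.

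A reader might also infer that the detectable effect is mis-stated. It is not: the protocol states a 0.02 difference and prints no detectable odds ratio.

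**Conclusion.** The point holds in limited form. On a scale capped at 100%, the STR proportion must be at least 0.905 at the printed values and at least 0.84 under any rounding, so 0.77 cannot be right. The non-STR proportion must be at least 0.80 at the printed values, so 0.74 is attainable only at the edge of rounding. The marginal probabilities behind the discordant pairs are therefore invalid, and the stated 80% power has no sound derivation. The direction and size of the effect on power are not determined, because the means and SD do not fix the discordance.

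This rests on two assumptions: that the cited measure is capped at 100%, and that the printed means and SD are the ones used. The inferred normal curve explains where the figures come from, but the bounds do not depend on it.

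**What to change.** In section 9.6, replace 0.74 and 0.77 with the proportions above 90% observed directly, either in the cited study or in the centers' electronic refill records, which the protocol already requires. If only means and SD are available, use a distribution bounded at 100% and name it. State whether the adherence measure is capped. Recompute and print the discordant fraction. Restate the power for a 0.02 difference at the planned 1030 pairs, in section 9.6 and in the synopsis, with a sensitivity range over plausible discordance. Enrolment, endpoint and analysis need not change.

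The cost is a short recalculation and rewording in two places. The downside is that a single power figure becomes a range that may be less favourable than 80%.

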- 2. Matching algorithm choice: The nearest neighbor algorithm or the nearest neighbor within a specified caliper distance algorithm will be used as a matching algorithm. The nearest neighbor matching selects for matching to a given STR subject the non-STR subject whose propensity score is closest to that of the STR subject. Nearest neighbor matching within a specified caliper distance is similar to nearest neighbor matching with the further restriction that the absolute difference in the propensity scores of matched subjects must be below some pre-specified threshold (the caliper distance) {27758} {27759}. The choice between one of these approaches will rely on how much data will be collected.
- 3. Sample balance diagnosis: Sample balance will be checked using the methods proposed by Ho et al. including standardized means, comparing higher-order moments, propensity-score summary statistics or empirical quantile-quantile plots for each variable {27772}.
- 4. Matching: Assign the matching membership and retain the propensity score for the case where further adjustment is needed.

Prescription errors sub-study

In this sub-study, unit of analysis will be a hospitalization episode of HIV-1 infected adult (due to any reason) in which there was a prescription of ART during the first 48 hours. Two cohorts will be considered: (i) STR and (ii) non-STR. Subjects will be enrolled that were hospitalised between 1st January 2012 and 29th December 2013.

For the prescription errors sub-study, subject selection will involve the following steps, to be initiated as soon as hospital approval has been granted at each site:

- 1. Search in the hospital registry to identify all hospitalization episodes of HIV-1 infected patients with admission date 1st January 2012 and 29th December 2013.
- 2. Check Inclusion criteria once identified, the Investigator will check whether those hospitalization episodes meet the inclusion criteria.

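### The stated 80% power for a 0.02 difference borrows discordance from patients compared with themselves; for the propensity-matched pairs planned here, power is about 18% to 32% if within-pair correlation lies between 0 and 0.5

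*Protocol*

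**What the plan says.** Section 9.6 of the protocol (Study Size, Adherence study) sizes the primary comparison to "achieve a power of 80% for detecting a difference of 0.02 in the proportion of patients with adherence > 90" per cent, "with a two sided test with a significance level of 0.05". The synopsis repeats the claim: "This is necessary to achieve a power of 80% for detecting a difference of 0.02".

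The method is a matched-pair one, driven by the number of discordant pairs. Discordance was estimated from a published study in which the same patients moved from non-STR to STR: average adherence was 97% beforehand and "after changing to an STR regimen a rate of 98" per cent. With a standard deviation of 11%, "a 0.74 and 0.77 proportion of adherent patients was estimated for non-STR and STR regimens, respectively". The discordant probability is then derived "if one assumes that patients who adhere to non-STR also adhere to the STR regimen". After allowances for 10 covariates, a 20% loss and 15% oversampling of non-STR, the target is 1030 pairs of patient-regimens after matching.

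Section 9.3 (Subject Selection) describes how pairs are formed. Matching is at patient-regimen level, and the nearest-neighbour step takes "the non-STR subject whose propensity score is closest to that of the STR subject". A subject may contribute regimens to both cohorts, but no rule pairs a subject with himself.

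**The concern.** In a matched-pair comparison of proportions, power for a given difference depends on how many pairs are discordant: the fewer, the higher the power. The section 9.6 assumption concerns one person under two regimens. It removes, or nearly removes, the pairs that are adherent only on non-STR, so discordance falls close to the difference itself.

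That may be reasonable for a before-and-after study. It has no basis when the two members of a pair are different people. A propensity score balances predictors of receiving STR; it does not make two patients' refill behaviour nearly identical. An adherent non-STR patient can easily be matched to a non-adherent STR patient.

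At stake is the stated power of the primary endpoint. If power at 0.02 is far below 80%, a non-significant result says little about a 2-point effect, yet the power statement invites the opposite reading.

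**Working it through.** **Inputs.** From section 9.6: difference d = 0.02, two-sided alpha 0.05, target power 80%, proportions 0.74 (non-STR) and 0.77 (STR), 1030 pairs. Not in the protocol: the within-pair correlation r of the binary outcome. It is assumed here, over 0 to 0.5.

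**Formulas.** With discordant fraction psi:

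- Pairs needed: n = [1.96·√psi + 0.842·√(psi − d²)]² / d²
- Power at n pairs: Φ{ [d·√n − 1.96·√psi] / √(psi − d²) }
- Discordance from margins and correlation: psi = p1(1 − p2) + p2(1 − p1) − 2r·√[p1(1 − p1)p2(1 − p2)]

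This is a McNemar approximation to the mixed or marginal models of section 9.8.

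**Step 1: the plan's own figures.** A normal distribution with mean 97 or 98 and SD 11 gives P(>90) = 0.738 and 0.766, matching 0.74 and 0.77. For d = 0.02, psi = 0.02 gives 390 pairs and psi = 0.03 gives 586. Adding 100 observations and dividing by 0.8 turns these into 613 and 858, so neither reaches 1030. A psi of 0.04 gives 783 pairs, and 783/0.8 + 50 = 1028. That would fit, but 0.04 is a reconstruction: the sentence that should carry the discordant probability is broken in the text at hand. No error is inferred from this. What follows needs only the stated margin, difference, alpha and pair count.

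**Step 2: different patients, 0.74 versus 0.76, 1030 pairs.** At r = 0:

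- psi = 0.74 × 0.24 + 0.26 × 0.76 = 0.1776 + 0.1976 = 0.3752
- d·√n = 0.02 × √1030 = 0.642; 1.96·√psi = 1.2005; √(psi − d²) = 0.612
- Power = Φ[(0.642 − 1.2005)/0.612] = Φ(−0.913) = 18.1%

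An ordinary two-proportion calculation with 1030 per group also gives 18.1%. Across the assumed correlations:

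| r | psi | Power at 1030 pairs | Pairs for 80% |
|---|---|---|---|
| 0 | 0.375 | 18.1% | 7,360 |
| 0.1 | 0.338 | 19.6% | 6,625 |
| 0.3 | 0.263 | 23.9% | 5,155 |
| 0.5 | 0.188 | 31.6% | 3,684 |

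**Step 3: correlation needed to rescue 80%.** Solving for 80% power at 1030 pairs gives psi = 0.0526. Then r = (0.3752 − 0.0526)/(2 × 0.1873) = 0.86.

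**Step 4: the larger difference between the plan's own margins, 0.74 versus 0.77.** At r = 0, psi = 0.74 × 0.23 + 0.26 × 0.77 = 0.3704 and power is 35.3%. At r = 0.3, psi = 0.260 and power is 47.2%.

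**Step 5: what 1030 pairs can detect.** Under independence, 80% power is reached at a difference of about 0.052, that is 0.74 versus 0.792 (odds ratio 1.34).

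**The case against.** The strongest counter-arguments are these.

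- **The correlation is unknown, and some pairs may be self-pairs.** This stands, so no single power figure should be quoted. One subject may supply regimens to both cohorts, and these share fixed baseline covariates, so nearest-neighbour matching could sometimes pair them. It does not restore the claim. If half of all pairs were self-pairs with discordance 0.04 and the rest independent, psi = 0.5 × 0.04 + 0.5 × 0.3752 = 0.2076 and power is about 29%.
- **McNemar is not the planned analysis.** True: section 9.8 names mixed or marginal models with propensity-score adjustment. Adjustment may change precision somewhat, but under independence the gap is about sevenfold in pairs (7,360/1030 = 7.1).
- **Confidence intervals are already planned.** Section 9.8 provides 95% intervals for parameters of interest, so part of the remedy exists. The power statement remains wrong.

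A reader might also infer more than the documents support:

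- *That the 0.02 target contradicts margins 0.03 apart.* With the discordance sentence broken, a second discordant cell may have been described: cells of 0.03 and 0.01, for instance, would give d = 0.02 and psi = 0.04. No contradiction can be shown.
- *That the margins are faulty because the implied normal curve runs above 100% adherence.* The protocol names no distribution, the source data are not available here, and proportions near 0.75 drive the result whatever their origin.
- *That true discordance is some fixed multiple of the value used.* The value used cannot be read, so no ratio can be given.

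**Conclusion.** The concern holds as an unsuitable design assumption. Discordance for patients compared with themselves was applied to pairs formed between patients, and the stated 80% power for 0.02 does not follow for the design described in section 9.3. With a base proportion of 0.74, two-sided 0.05 and 1030 pairs, power at 0.02 is about 18% to 32% for within-pair correlations of 0 to 0.5, and about 35% to 47% at a difference of 0.03 for correlations of 0 to 0.3. The correlation range is an assumption and the calculation approximates the planned model. The conclusion is not sensitive to either, since 80% would need a correlation near 0.86, which propensity matching of different people cannot plausibly produce. It would be tempting to report flatly that the study has 18% power; the documents do not support that, because 18% is the zero-correlation case only.

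**What to change.** In section 9.6 and the synopsis (Study Size):

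1. Replace the claim of 80% power at 0.02 with power computed from discordance for different patients, naming the assumed within-pair correlations and showing the range (about 18% at 0, 24% at 0.3, 32% at 0.5).
2. State that 1030 pairs give 80% power for a difference of about 5 points (0.74 versus about 0.79) under independence.
3. State that the primary result will be interpreted by its confidence interval, so that non-significance is not taken as evidence against a 2-point difference.

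This is rewording in two places. It asks for no additional subjects, data or analyses. The cost is a less favourable stated figure.

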9.7. Data Management

For each subject enrolled, investigators will record the data (collected from subject's clinical files and prescription / laboratory / pharmacy files) into an electronic Case Report Form (eCRF) specifically designed for this study. Each investigator will be assigned with a unique log-in and password for accessing the eCRF.

Investigators should keep source documentation for each subject included in the study, consisting of case and consultation notes (hospital, clinic medical records or patient diary) containing demographic and medical information, results of any tests or assessments performed as part of routine clinical practice, and pharmacy refill and prescription errors information.

All data will be kept anonymous during this process.

A Data Management Unit will be responsible for designing and validating the web-based eCRFs. A detailed data validation plan that will identify missing data, out-of-range data, and other data inconsistencies will be implemented in the electronic platform prior to study start.

Once all information is introduced in the database, data will be reviewed. Queries will be prepared in case data inconsistencies are found and will be resolved by each investigator. After the data validation, the database will be locked and sent to a Statistics Unit in order to perform the statistical analysis and report.

